3.7.3.5 Pregnancy Test

(1) Time points

At screening, the initiation and Week 8 (or discontinuation) of the antidepressant treatment period (Phase A), Week 6 (or discontinuation) of the double-blind period (Phase B), and Week 6 (or discontinuation) of the antidepressant-responder treatment-continuation period (Phase A+)

(2) Methods

A urine pregnancy test will be performed in women of childbearing potential^a and the date of urine sampling and the result of the test will be recorded in the source documents and the CRF. If the urine test is positive, another pregnancy test will be performed using serum [excluding the time of screening and the initiation of the antidepressant treatment period (Phase A)] and the date of blood sampling will be recorded in the source documents and the CRF. A serum pregnancy test will be performed by the central laboratory selected by the sponsor. For appropriate procedures for the collection, handling, and shipment of samples, separately documented procedures will be prepared and provided prior to the start of the trial. The central laboratory will report the results of tests to the investigator or subinvestigator. The investigator or subinvestigator will confirm the results of tests and date and sign the clinical laboratory test report to make it an official document. The results of serum tests, which will be reported directly from the central laboratory to the sponsor as an electronic file, do not need to be recorded in the source documents or the CRF.

^{a:} Women of childbearing potential are defined as female subjects for whom menstruation has started and who are not documented as sterile (ie, have had a bilateral oophorectomy and/or hysterectomy or who have been postmenopausal for at least 12 months).

3.7.3.6 Columbia-Suicide Severity Rating Scale

(1) Time points

At screening, the initiation and Weeks 1, 2, 3, 4, 6, and 8 (or discontinuation) of the antidepressant treatment period (Phase A), Weeks 1, 2, 3, 4, 5, and 6 (or discontinuation) of the double-blind period (Phase B), post-treatment observation period, and Weeks 1, 2, 3, 4, 5, and 6 (or discontinuation) of the antidepressant-responder treatment-continuation period (Phase A+)

(2) Methods

This scale consists of the "Baseline Version," which assesses the lifetime history of suicide-related events and suicidal ideation and the "Since Last Visit Version," which focuses on suicidality since the last assessment in the trial. The "Baseline Version" will be used at screening and the "Since Last Visit Version" will be used at subsequent time points for C-SSRS assessment. The date, time, and results of assessment will be recorded in the source documents and the CRF.

The presence of suicidal ideation 1 or 2 will be assessed with "yes" or "no," and if the answer to 2 is "yes," suicidal ideation 3 to 5 will be assessed. If the answer to suicidal ideation 1 or 2 is "yes," the intensity of ideation will also be rated. Intensity of ideation will be rated on a 5-point scale for "frequency" and "duration" and a 6-point scale for "controllability," "deterrents," and "reasons for ideation." The following suicidal behavior will also be assessed with "yes" or "no," and the total numbers of each suicide attempt will be recorded. If there is an actual attempt, "actual lethality/physical damage" will be rated on a 6-point scale, and if actual lethality/physical injury is 0, "potential lethality" will be rated on a 3-point scale.

Suicidal ideation: 1. Wish to be dead 2. Non-specific active suicidal thoughts

- 3. Active suicidal ideation with any methods (not plan) without intent to act
- 4. Active suicidal ideation with some intent to act, without specific plan
- 5. Active suicidal ideation with specific plan and intent

Suicidal behavior: Actual attempt Non-suicidal self-injurious behavior Interrupted attempt Aborted attempt Preparatory acts or behavior Suicidal behavior Suicide (only for "Since Last Visit Version")

3.7.3.7 Drug Induced Extra-Pyramidal Symptoms Scale

(1) Time points

At Week 8 of the antidepressant treatment period (Phase A), Weeks 1, 2, 3, 4, 5, and 6 (or discontinuation) of the double-blind period (Phase B), and Week 6 (or discontinuation) of the antidepressant-responder treatment-continuation period (Phase A+)

(2) Methods

The investigator or subinvestigator will assess the following 9 items related to extrapyramidal symptoms on a 5-point scale ranging from 0 (none, normal) to 4 (severe) using DIEPSS at specified time points. The date, time, and results of assessment will be recorded in the source documents and the CRF.

| 1. Out 2. Dradykinosia 5. Statoffica 4. Masole figlally 5. From | 1. Gait | Bradykinesia | Sialorrhea | 4. Muscle rigidity | Tremor |
|---|---------|--------------------------------|------------------------------|--------------------|--------------------------|
|---|---------|--------------------------------|------------------------------|--------------------|--------------------------|

6. Akathisia 7. Dystonia 8. Dyskinesia 9. Global severity

3.7.3.8 Abnormal Involuntary Movement Scale

(1) Time points

At Week 8 of the antidepressant treatment period (Phase A), Week 6 (or discontinuation) of the double-blind period (Phase B), and Week 6 (or discontinuation) of the antidepressant-responder treatment-continuation period (Phase A+)

(2) Methods

Using AIMS, the investigator or subinvestigator will assess the severity of abnormal involuntary movement at 7 sites ("muscles of facial expression," "lips and perioral area," "jaw," "tongue," "upper extremities [arms, wrists, hands, and fingers]," "lower extremities [legs, knees, ankles, and toes]," and "neck, shoulders, and hips") and 3 global judgment items on a 5-point scale ranging from 0 (none) to 4 (severe) and assess the dental status items "current problems with teeth and/or dentures" and "Dose patient usually wear dentures" as either "yes" or "no," at the specified time points. The date, time, and results of assessment will be recorded in the source documents and the CRF.

3.7.3.9 Barnes Akathisia Rating Scale

(1) Time points

At Week 8 of the antidepressant treatment period (Phase A), Week 6 (or discontinuation) of the double-blind period (Phase B), and Week 6 (or discontinuation) of the antidepressant-responder treatment-continuation period (Phase A+)

(2) Methods

Using BARS, the investigator or subinvestigator will assess "objective," "subjective—awareness of restlessness," and "subjective—distress related to restlessness" for akathisia on a 4-point scale and a "global clinical assessment of akathisia" on a 6-point scale at the specified time points. The date, time, and results of assessment will be recorded in the source documents and the CRF.

3.7.4 Prior and Concomitant Medications and Therapies

The investigator or subinvestigator will examine the use of the following prior and concomitant medications and therapies. For prior and concomitant medications, the name of the drug, purpose of use (excluding prior medications used to treat the current major depressive episode), dose, frequency, route of administration, start and end dates of treatment, and treatment response (for prior medications used to treat the current major depressive episode) will be examined and recorded in the source documents and the CRF. For prior and concomitant therapies, the name of the therapy, purpose of use (excluding prior therapies used to treat the current major depressive episode), and the start and end dates of treatment will be examined and recorded in the source documents and the CRF.

- Prior medications and therapies
 - Prior medications used to treat the current major depressive episode (all antidepressants)
 - Prior therapies used to treat the current major depressive episode (psychotherapies/somatic therapies up until 6 weeks before informed consent)
 - All prior medications and therapies used within 30 days before acquisition of informed consent
- Concomitant medications and therapies
 - Concomitant medications and therapies used during the trial period (including treatments for AEs)

3.7.5 Investigational Medicinal Product

(1) Treatment compliance

The investigator or subinvestigator will confirm the subject's IMP compliance during the interval between 2 consecutive scheduled visits after proceeding to the antidepressant treatment period (Phase A) and record the consumed daily dose and the start and end dates of IMP administration in the source documents and the CRF.

(2) Compliance rate

Compliance rate (%) = $\frac{\text{Doses consumed between 2 consecutive scheduled visits (number of tablets)}}{\text{"Number of prescribed days between 2 consecutive scheduled visits" (number of days)}} \times 100$

(3) Compliance instruction

The investigator, subinvestigator, or IMP manager will provide subjects with compliance instructions with particular attention to the following points:

- The subject should take the IMP once daily, removing only the prescribed daily amount of the IMP from the sheet.
- The subject must bring any missed/unused doses (IMP tablets) to the trial site at the next visit.
- Contact information for any questions about taking the IMP
- The subject must not discard any empty IMP sheets but should bring them to the trial site at the next visit.
- The subject should be withdrawn from the trial if the subject's IMP compliance during an interval between 2 consecutive scheduled visits is less than 65%.

3.7.6 Requisite Concomitant Medication

The investigator or subinvestigator will confirm the subject's compliance with the requisite concomitant medication, a commercially available antidepressant (SSRI or SNRI), during the interval between 2 consecutive scheduled visits after proceeding to the antidepressant treatment period (Phase A) and record the name of the drug, prescribed daily dose, consumed daily dose, and start and end dates of administration in the source documents and the CRF.

3.7.7 Pharmacokinetic Assessment, Pharmacogenomic Assessment, and

3.7.7.1 Pharmacokinetic Assessment

Plasma brexpiprazole concentrations will be measured by validated high performance liquid chromatography/tandem mass spectrometry. Metabolites that are not presented in the protocol may be measured based on newly obtained information.

The bioanalytical laboratory will measure drug concentrations only for samples collected from subjects in the brexpiprazole 1 mg/day group or the brexpiprazole 2 mg/day group after recording the use of the documents providing treatment assignment codes. Access to the documents containing treatment assignment codes will be strictly controlled and not

disclosed to anyone other than those who need them to carry out trial-related activities in the opinion of the person responsible for drug concentration measurements. The bioanalytical laboratory will hold the results of drug concentration measurements in strict confidence and submit an electronic file containing these results to the sponsor after unblinding.

3.7.7.1.1 Blood Sampling Time Point

3.7.7.1.2 Plasma Samples for Pharmacokinetic Assessment

All plasma samples will be shipped to the bioanalytical laboratory. The date and time of IMP administration immediately before blood sampling and the date and time of blood sampling will be recorded in the source documents and the CRF. The results of measurements, which will be reported directly from the bioanalytical laboratory to the sponsor as an electronic file after unblinding, do not need to be recorded in the source documents or the CRF. Detailed handling and shipping methods of samples are provided in Appendix 1.

3.7.7.2 Pharmacogenomic Assessment

3.7.7.2.1 CYP2D6 Genetic Testing

CYP2D6 genotypes and phenotypes will be analyzed. CYP2D6 genetic testing is mandatory.

The CYP2D6 genotype will be determined for each subject based on the CYP2D6 genotyping table (Appendix 2). In addition, based on the CYP2D6 genotype, the phenotype will be classified into the following 4 types: extensive metabolizer (EM), intermediate metabolizer (IM), poor metabolizer (PM), and unknown. The results of CYP2D6 genetic testing will not be disclosed to subjects.

The genetic analysis laboratory will select blood samples collected from subjects in the brexpiprazole 1 mg/day group and the brexpiprazole 2 mg/day group and extract DNA after recording the use of the documents providing treatment assignment codes. Blood samples collected from subjects in the placebo group will be discarded in accordance with the procedure specified by the genetic analysis laboratory. Access to the documents containing treatment assignment codes will be strictly controlled and not be disclosed to anyone except for those who need them to carry out trial-related activities in the opinion of the person responsible for genetic testing. The genetic analysis laboratory will hold the

[figure not shown]
results of CYP2D6 genetic testing in strict confidence and submit an electronic file containing these results to the sponsor after unblinding.

[figure not shown]
3.7.7.2.1.1 Blood Sampling Time Point

[figure not shown]
Blood sampling will be performed at Week 6 of the double-blind period (Phase B) or at discontinuation. If resampling of blood is necessary, it will be performed by the end of the trial date.

[figure not shown]
3.7.7.2.1.2 Samples for CYP2D6 Genetic Testing

All blood samples will be shipped to the genetic analysis laboratory. The date and time of blood sampling will be recorded in the source documents and the CRF. The results of measurements, which will be reported directly from the genetic analysis laboratory to the sponsor as an electronic file after unblinding, do not need to be recorded in the source documents or the CRF. Detailed handling and shipping methods of samples are provided in Appendix 1.

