Treatment compliance regarding IMP and requisite concomitant medication will be recorded.

Concomitant drugs/

Pregnancy tests will be performed only in female subjects of childbearing potential.

d For this item, subjects will be asked to visit the trial site in a fasting state (a fast for at least 8 hours [including drinks containing sugar, such as juice]) at Week 8 of the antidepressant treatment period (Phase A), and in a fasting state to the extent possible at other times, including at the discontinuation examination.

| Table 3.7-2 | Schedule of Assessments (Double-blind Period [Phase B]) | | | | | | | B]) |
|--|---|----------------------|----------------------|----------------------|----------------------|----------------------|----------------------------|---|
| Test Period (Acceptable Window) | p 11 11: 1p : 1/pt p b | | | | | | | Post- treatment Observation Period |
| | Week 1 (± 1 day) | Week 2 (± 2 days) | Week 3 (± 2 days) | Week 4 (± 2 days) | Week 5 (± 2 days) | Week 6 (± 2 days) | At discontin- uation | After 30 days ^g (± 5 days) |
| MADRS | • | • | • | • | • | • | • | |
| CGI-I | • | • | • | • | • | • | • | |
| CGI-S | • | • | • | • | • | • | • | |
| HAM-D | | | | | | • | • | |
| SDS | | | • | | | • | • | |
| MADRS-S questionnaire | • | • | • | • | • | • | • | |
| Laboratory tests | | | • | | | • ^d | • | |
| Vital signs | • | • | • | • | • | • | • | |
| Physical examinations | • | • | • | • | • | • | • | • |
| Waist circumference | | | | | | • | • | |
| Body weight | | | | | | • | • | |
| 12-lead ECG | | | | | | • | • | |
| Pregnancy test | | | | | | • e | e | |
| C-SSRS | • | • | • | • | • | • | • | • |
| DIEPSS | • | • | • | • | • | • | • | |
| AIMS | | | | | | • | • | |
| BARS | | | | | | • | • | |
| | | | , | , | , | | | , |
| Blood sampling for CYP2D6 genetic testing | | | | | | • | • | |
| | | | | | | | | |
| Adverse events | ← | | | | | | | ←→ |
| IMP and requisite concomitant medication a | • | • | • | • | • | • | • | |
| Concomitant drugs/ therapies | ← | | | | | | → | ← → |

PK = pharmacokinetics

Pregnancy tests will be performed only in female subjects of childbearing potential.

Treatment compliance regarding IMP and requisite concomitant medication will be recorded.

The starting point of the double-blind period (Phase B) is the day of assessment at Week 8 of the antidepressant treatment period (Phase A).

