3.7.3.2 Clinical Laboratory Assessments

(1) Time Points

At screening (in the fasting state to the extent possible), Week 8 (in the fasting state) or at discontinuation (in the fasting state to the extent possible) of the antidepressant treatment period (Phase A), Week 3 (in the fasting state to the extent possible) and Week 6 (in the fasting state) or at discontinuation (preferably in the fasting state) of the double-blind period (Phase B), and Week 6 (in the fasting state) or at discontinuation (in the fasting state to the extent possible) of the antidepressant-responder treatment-continuation period (Phase A+)

(2) Methods

Subjects will be asked to visit the trial site in the fasting state (a fast for at least 8 hours [including drinks containing sugar, such as juice]) at Week 8 of the antidepressant treatment period (Phase A) and Week 6 of the double-blind period (Phase B) or the antidepressant-responder treatment-continuation period (Phase A+) and in the fasting state to the extent possible at other time points including examinations at discontinuation.

Blood and urine samples will be collected from each subject at the time of clinical laboratory tests as specified in the assessment schedules shown in Table 3.7-1 through Table 3.7-3, and the date and time of blood sampling and the date of urine sampling as well as the fasting or fed state during blood sampling will be recorded in the source documents and the CRF. In this trial, the central laboratory selected by the sponsor will be used. Clinical laboratory test values determined at the central laboratory will be used for eligibility assessment. For appropriate procedures for the collection, handling, and shipment of samples, separately documented procedures will be prepared and provided prior to the start of the trial. The central laboratory will report the results of tests to the investigator or subinvestigator. The investigator or subinvestigator will confirm the results of tests and date and sign the clinical laboratory test report to make it an official document. The results of laboratory tests, which will be reported directly from the central

laboratory to the sponsor as an electronic file, do not need to be recorded in the source documents or the CRF.

| Table 3.7.3.2-1 Clinical Laboratory Assessments | | | | |
|---|---|--|--|--|
| Hematology: | Serum chemistry: | | | |
| Red Blood Cell count | AST (Glutamic oxaloacetic transaminase [GOT]) | | | |

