8.3 Subgroup Analyses

For the change from baseline (Week 8 of the antidepressant treatment period [Phase A]) in MADRS total score, the same MMRM analysis as that of the primary endpoint will be performed for each of the following subgroups.

For CYP2D6 phenotype, all subjects in the placebo group will be included in each subgroup.

- Requisite concomitant medication (duloxetine, escitalopram, fluvoxamine, milnacipran, paroxetine, sertraline, venlafaxine)
- Sex (male, female)
- Age (< 55 , ≥ 55)
- Number of adequate antidepressant drug treatments (1, 2, 3)
- DSM-5 diagnosis (single episode, recurrent episode)
- Frequency of major depressive episodes (1, 2, ≥ 3)
- Duration (in months) of the current episode (\leq median, $>$ median)
- Baseline MADRS total score (\leq median, $>$ median)

- Concomitant use of ultrashort-acting sedative-hypnotic drugs in the double-blind period (Phase B) (yes or no)
- Body weight (\leq median, $>$ median)
- BMI (\leq median, $>$ median)
- CYP2D6 phenotype (IM, EM)
- Impact of COVID-19 pandemic (subjects from whom consent was obtained before 07 Apr 2020, those from whom consent was obtained on or after 07 Apr 2020)

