9.2.2 Subgroup Analysis of Adverse Events

Numbers and proportions of subjects with TEAEs will be summarized by SOC and PT by treatment group and for the overall brexpiprazole group in each of the following subgroups:

- Requisite concomitant medication (duloxetine, escitalopram, fluvoxamine, milnacipran, paroxetine, sertraline, venlafaxine)
- Sex (male, female)
- Age (< 55, ≥ 55)
- CYP2D6 phenotype (IM, EM, PM, Unknown)

- Impact of COVID-19 pandemic (subjects from whom consent was obtained before 07 Apr 2020, those from whom consent was obtained on or after 07 Apr 2020)

9.2.3 Adverse Events in the Antidepressant Treatment Period (Phase A) and the Antidepressant-responder Treatment-continuation Period (Phase A+)

Numbers and proportions of subjects who experienced AEs in the antidepressant treatment period (Phase A) will be summarized by SOC and PT overall and for each requisite concomitant medication in the ADT set.

Numbers and proportions of subjects who experienced AEs in the antidepressant-responder treatment-continuation period (Phase A+) will be summarized by SOC and PT overall and for each requisite concomitant medication in the Phase A+ set.

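### The CYP2D6 sample is taken only at Phase B Week 6 or at discontinuation, so brexpiprazole subjects who miss that examination fall out of the IM/EM efficacy subgroups while all placebo subjects stay in

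*Protocol*

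**What the plan says.** - **Sampling time.** Protocol 3.7.7.2.1.1 states: "Blood sampling will be performed at Week 6 of the double-blind period (Phase B) or at discontinuation". In Table 3.7-2 the row "Blood sampling for CYP2D6 genetic testing" is marked in those two columns only. Weeks 1 to 5 and the post-treatment visit carry no mark.
- **Repeat samples.** The same section adds: "If resampling of blood is necessary, it will be performed by the end of the trial date".
- **Status.** Protocol 3.7.7.2.1 says "CYP2D6 genetic testing is mandatory", and Protocol 3.4.1 bars anyone who does not consent to it. The phenotype classes are extensive metabolizer (EM), "intermediate metabolizer (IM), poor metabolizer (PM), and unknown". Only brexpiprazole samples are typed; placebo samples are discarded.
- **Discontinuation examination.** Protocol 3.7.1.8 requires it for withdrawn subjects, but Protocol 3.7.1.9 gives it no fixed window. Protocol 3.8.3.3 and 3.11 provide for withdrawal of consent and loss to follow-up.
- **Use of the phenotype.** Protocol 6.2 planned a listing only. SAP 14 records the change: phenotype is now tabulated with the baseline characteristics (SAP 7.2) and used in efficacy and safety subgroups.
- **Levels.** SAP 8.3 has two levels for the MADRS model, IM and EM, with the whole placebo group in both. SAP 9.2.2 (adverse events) and SAP 10 (pharmacokinetics) have four: IM, EM, PM and Unknown.
- **Blood already drawn.** Protocol 3.7.3.2 says "Blood and urine samples will be collected from each subject at the time of clinical laboratory tests", and Phase A Week 8 is one of those times.

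**The concern.** Genotype is fixed before randomisation, and the SAP reports phenotype among the baseline characteristics. Under this schedule, whether it is known depends on what happens after randomisation, namely whether the subject reaches Week 6 or attends a discontinuation examination.

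The effect is one-sided in the efficacy subgroups. A brexpiprazole subject who stops and is not sampled has no phenotype and enters neither the IM nor the EM model. A placebo subject who stops in the same way enters both. Each subgroup then compares brexpiprazole subjects who had to be sampled late in the trial with a placebo group that had no such condition. That weakens a subgroup reading that is meant to show whether the effect differs by metabolic status.

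In the adverse event and pharmacokinetic summaries the loss is milder. An unsampled subject can still be shown, but not under a true phenotype.

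**Working it through.** **1. The plan's own figure.** The only stated sample size is the overall one (Protocol 7.1, SAP 4). With a difference of 2.4, SD 7.7, two-sided 0.05 and 90% power, n per group = 2 × (1.960 + 1.282)² × 7.7² / 2.4², which rounds up to 217. The t-based solution is 217.3, rounded up to 218, as stated; power at 218 is 0.902. Allowing for 7% discontinuation, 218 / 0.93 = 234.4, so 235, and 240 covers it. No CYP2D6 analysis has a stated sample size, and none of these figures depends on when the CYP2D6 sample is drawn.

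**2. Where an unsampled subject goes.**

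| Analysis | Levels | Unsampled brexpiprazole subject | Placebo subject |
|---|---|---|---|
| MADRS model (SAP 8.3) | IM, EM | excluded | in both subgroups |
| Adverse events (SAP 9.2.2) | IM, EM, PM, Unknown | at best Unknown | never typed |
| Pharmacokinetics (SAP 10) | EM, IM, PM, Unknown | at best Unknown | not applicable |

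The efficacy row is confined to the full analysis set. The imbalance therefore bites for subjects with at least one MADRS score after the start of Phase B treatment; those without one are out of the model in every arm. For pharmacokinetics, the SAP table titles place the concentrations at Week 3, so a subject lost after that can have a concentration without a phenotype.

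**3. How many subjects.** Inputs: 240 per group, hence 480 on brexpiprazole, and 7% discontinuation (Protocol 7.1). Expected brexpiprazole discontinuers = 480 × 0.07 = 33.6, about 34. The share who give no sample is not in the documents, so the whole range is shown.

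| Assumed share of discontinuers not sampled | Untyped (33.6 × share) | Of 480 |
|---|---|---|
| 0% | 0 | 0% |
| 10% | 3.4, about 3 | 0.7% |
| 25% | 8.4, about 8 | 1.75% |
| 50% | 16.8, about 17 | 3.5% |
| 100% | 33.6, about 34 | 7% |

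At the same rate, 240 × 0.07 = 16.8, about 17 placebo subjects stop early. All of them who are in the full analysis set remain in both subgroups.

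**4. How many would stop for adverse events.** The overseas rates of adverse events leading to discontinuation were 1.3% at 1 mg (Protocol 1.2.2.1) and 2.1% to 3.2% at 2 mg (Protocol 1.2.2.2 and 1.2.2.3). Applied here: 240 × 0.013 = 3.1, plus 240 × 0.021 = 5.0 to 240 × 0.032 = 7.7. The total is about 8 to 11 of 480, before any allowance for those who are sampled at discontinuation.

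**The case against.** Four arguments stand against making much of this.

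*Most phenotype displays keep these subjects.* A reader might infer that untyped subjects disappear from the phenotype analyses altogether. They do not: the protocol has an unknown class, and the SAP carries an Unknown level for adverse events and concentrations. Exclusion is certain only in the IM/EM MADRS subgroups. This stands, with one gap: the available text does not say whether unknown covers subjects who were never sampled or only indeterminate genotypes.

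*The plan pursues those who stop.* A reader might also infer that subjects with high exposure who stop for intolerance are the likeliest to be untyped, so that early stopping or adverse events in IM and PM subjects are understated. The documents do not support this. Withdrawn subjects are to have the discontinuation examination, which includes this sample (Protocol 3.7.1.8). Adverse events that lead to stopping are to be followed (Protocol 3.8.3.2), and a retention discussion is required (Protocol 3.8.3.4). No phenotype frequencies are given, nothing links stopping to phenotype, and no planned table shows discontinuation by phenotype. This stands in full.

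*Resampling may rescue some.* The provision runs to the end of the trial date, but it reads as repeating a sample already drawn. Whether it permits a late first sample is unclear.

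*The remedy is not entirely free.* Eligibility for Phase B is decided at the Week 8 visit, where the laboratory blood is also drawn, and the order is not fixed. Genetic testing has its own consent, and the text does not say whether a stored tube could be typed after consent is withdrawn. Both points stand, but both are small. The Phase B entry criteria (Protocol 3.4.2, items 9 to 12) need no laboratory result, so the decision can come before the draw.

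**Conclusion.** The point holds in a narrow form. Because the sample is drawn only at Week 6 or discontinuation, some brexpiprazole subjects may have no genotype. They are then left out of the IM and EM MADRS subgroups while every placebo subject in the full analysis set is kept. That comparison is not like for like, although the direction of any bias cannot be read from the documents. Elsewhere the consequence is at most a count under Unknown.

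The size is uncertain: 0 to about 34 of 480, resting on the planned 7% discontinuation and an unstated share who miss the sample. The primary analysis and the sample size are unaffected. This is a worthwhile improvement to a secondary use of the data, not a flaw in the main comparison.

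**What to change.** In Protocol 3.7.7.2.1.1 and the schedules of assessments (Tables 3.7-1 and 3.7-2), move the CYP2D6 sample to the Phase A Week 8 visit, which is also the starting day of Phase B. Draw it alongside the laboratory blood once Phase B eligibility has been decided, or draw it regardless and discard the tube if the subject enters Phase A+. Keep Week 6 or discontinuation for a repeat sample or a missed first one, and say so explicitly.

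In the SAP, state how never-sampled subjects are classified and report their number by brexpiprazole arm. If sampling is already complete, this part can still be done.

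The cost is a schedule and laboratory manual edit, plus either an ordering constraint at Week 8 or a few discarded tubes. No visit is added. Results can stay undisclosed until unblinding, and placebo samples can still be discarded, as Protocol 3.6 and 3.7.7.2.1 now provide.
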